5.2 Imaging Protocols - ^{11}C Choline PET/CT/MRI

1. ^{11}C choline PET/CT Imaging Protocol:
 - Patient should hydrate with 16 ounces of water prior to the imaging study
 - Fasting is required for at least 6 hours
 - Void prior to study
 - 15 - 20 mCi ^{11}C -choline IV Injection
 - 5 min delay after injection.
 - PET images skull base to mid thigh with 3 min per bed position
 - Image acquisition order changed due to bladder filling
 - If CT before MRI, then images obtained top to bottom
 - If MRI before CT, then images obtained bottom to top
 - CT skull base to mid thigh for attenuation correction
 - Use of IV contrast, if applicable, based on ACR IV contrast guidelines renal function screening protocol
 - Slice thickness 2.5, kvp 120, mA 100, exposure time 500, 80 - 100 cc contrast
 - Fusion of PET and CT images

2. MRI whole body imaging protocol:
 - No IV contrast
 - High resolution axial T2 prostate bed, axial DWI pelvis, coronal T2 skull base to mid thighs
 - Fusion of coronal and PET images

5.3 Imaging Technology

The imaging studies referenced above will be conducted as defined in Section 5.2 above. The CT and MR studies must be performed as one continuous procedure using the GE Trimodality PET Imaging System. This will require the patient to be immobile for approximately 60 minutes as each imaging study is executed.

The GE Trimodality PET Imaging System consists of the following integrated equipment: GE Discovery PET/CT 7.0 Imaging System, a GE Discovery MR750w 3.0T Imaging System, and the Lateral Docking Trimodality Patient Transporter. This system will allow for the combined imaging of PET, CT, and MR modalities in one integrated session using the Lateral Docking Transporter to ensure image synchronization between the modalities.

5.4 Imaging Review and Interpretations

5.4.1 Image Review

There will be two aspects to the evaluation, interpretation and use of the imaging data that is produced as part of this study. First, the information will be used immediately by the primary treatment physician to best assess the patient's status and select a therapy regimen. Second, at the end of the study, all of the patient data will be gathered for a comprehensive review which will proceed as follows:

1. Each patient will be assigned a research participant number at the time of consent.
2. This participant number will be substituted for all patient identifying information, where possible.
3. Any remaining patient identification information will be scrubbed from the patient files.
4. The patient identifier key will be stored on a password protected computer at DMH.
5. Access to this identifier key will be restricted from any of the data reviewers.
6. Scrubbed patient images with the identifier will be saved to a compact disc for radiologist review.
7. Studies will be presented in a random order for analysis.

8. The imaging studies will be interpreted by board certified radiologists:
 - a. Dr. [name]
 - b. Dr. [name]
 - c. Dr. [name]
9. Worksheets will be saved in a locked cabinet at DMH. The worksheets will be scanned and added to the secure computer study database.
10. The imaging reviews will be compared to the histological data or post-treatment imaging data for statistical analysis.

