5. Patients entered into the study will undergo a ^{11}C -choline PET CT scan and MRI scan. The CT scan will be performed with intravenous contrast unless deemed unsafe by lab values. The CT and MRI images will be evaluated for evidence of metastatic prostate cancer. The ^{11}C -choline PET CT and MRI images will be evaluated for evidence of metastatic prostate cancer. Unequivocal evidence of metastasis on both conventional imaging and ^{11}C -choline PET will be considered a true positive. Evidence of metastasis on conventional imaging or ^{11}C -choline PET will be confirmed with biopsy or surgical pathology when possible, or by response to treatment on subsequent imaging. If confirmation of metastasis is not achievable by biopsy or surgical pathology, then confirmation will be achieved with ^{11}C -choline PET CT and MRI images obtained 3 months after treatment conclusion. Rates of confirmed metastasis between conventional CT and MRI images will be compared with the ^{11}C -choline PET CT and MRI images.
6. Upon conclusion of each imaging protocol, the referring physician will receive written documentation of the results. At this time, the patient will be considered off study and no further follow up is required.

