5.5 Study Data – Statistical Analysis

- Sample Size:

This study is designed to compare fused ¹¹C-choline PET/CT and MRI scans against a standard CT scan and MRI scan. Based on the literature, the group detection rates are approximately 50%. In this study a 20 percentage point increase (eg: from 15 – 35 percent) in detection rate is the desired goal. The study is a paired design, in that each procedure will be performed on each individual. The important performance characteristics of these tests, including sensitivity, specificity, positive predictive value, and negative predictive value will be examined within this study. A sample size estimate was derived using a p-value of 0.05, a power of 80 %, and a paired chi square test for proportions. It was further assumed that the false positive rate is about 4 % and the false negative rate is about 20 %, which are similar to the literature. This would indicate approximately 66 pairs of data. To compare, an independent chi square test would indicate about 71 subjects per group for a comparable 20 point change. Increasing the sample size by 10 percent, for attrition, would increase the number of paired samples to about 73. Increasing the number of pairs to 100 will provide some flexibility on the false positive and false negative rates.

While more than 100 patients may be admitted into the study under expanded access, for the purposes of the comparison study and resulting data analysis, only the first 100 qualified patients will be admitted into the study and included in the study data.

- Data Analysis:

1. True positives will consist of evidence of metastatic prostate cancer on conventional CT or MRI images or on ¹¹C-choline PET/CT or MRI images confirmed with biopsy, surgical

pathology, or by response to treatment with androgen suppression or other medical or radiation therapy.

2. True negatives will consist of negative images.
3. False positive will consist of evidence of metastatic prostate cancer on conventional CT or MRI images or on ^{11}C -choline PET/CT or MRI images, but without corresponding confirmation from biopsy, surgical pathology or response to treatment.
4. False negative will consist of negative images, but with positive biopsy, surgical pathology or a response to treatment.
5. Sensitivity, specificity, PPV, and NPV of CT and MRI and of ^{11}C -choline PET/CT and MRI will be calculated
6. Performance characteristics between ^{11}C -choline PET/CT and PET/MRI will be compared.

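### A lesion called only on the end-of-study read cannot prompt confirmation, and 5.5 item 3 scores it a false positive unless existing data happen to confirm it

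*Combined protocol and SAP*

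**What the plan says.** All references are to the comparison-study protocol, the first of the two protocols in the combined file.

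- **Two uses of the images (5.4.1).** The first is clinical: "First, the information will be used immediately by the primary treatment physician to best assess the patient's status and select a therapy regimen". The second is the research review, which is placed after the study: "Second, at the end of the study, all of the patient data will be gathered for a comprehensive review which will proceed as follows". The images are de-identified, presented in random order and read by board-certified radiologists.
- **Which read is scored (5.4.1 item 10).** "The imaging reviews will be compared to the histological data or post-treatment imaging data for statistical analysis". The imaging reviews here are the end-of-study reads.
- **Follow-up (5.1 item 6).** Once the referring physician has the written result, "At this time, the patient will be considered off study and no further follow up is required".
- **Confirmation (5.1 item 5).** Evidence of metastasis on conventional imaging or on PET "will be confirmed with biopsy or surgical pathology when possible, or by response to treatment on subsequent imaging". Where pathology is not achievable, it rests on repeat PET CT and MRI "images obtained 3 months after treatment conclusion". The text does not say which of the two reads starts this process.
- **Scoring (5.5 Data Analysis item 3).** A false positive is evidence of metastasis on either kind of imaging, "but without corresponding confirmation from biopsy, surgical pathology or response to treatment". There is no category for a positive that was never assessed.

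**The concern.** The test result and the reference standard are tied to different reads. The confirmatory data grow out of care that follows the immediate clinical report. The 2×2 tables are filled from a later read that returns nothing to the people who could confirm a finding: 5.4.1 has no feedback step, and item 5 keeps the identifier key from the reviewers.

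When the two reads differ, a lesion seen only at the study read has no route of its own to confirmation. Item 3 then treats absence of evidence as evidence of error. A true lesion can be booked as a mistake of the test when all that happened is that two reads disagreed and the work-up had closed. The problem would remain even if every clinically reported lesion were fully verified.

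At stake are PPV and specificity for each modality (objective B), the rates of confirmed metastasis compared under 5.1 item 5, and the paired comparison in 5.5.

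**Working it through.** **1. Figures that are not in dispute.** The 66 pairs in 5.5 reproduce if 20% and 4% are taken as the two discordant proportions (two-sided 0.05, 80% power): (1.960 + 0.842)² × (0.24 − 0.16²) / 0.16² = 65.7. On that reading about 24 men in 100 are discordant, so moving even a few men matters to a paired test.

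**2. Path of a late call.**

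| Step | Place | Consequence |
|---|---|---|
| Report sent, care chosen | 5.4.1, first use; 5.1 item 6 | Patient off study |
| Confirmatory data arise | 5.1 item 5 | Driven by what was known at that time (inference) |
| Scored read | 5.4.1 items 7–10 | After all data are gathered |
| Lesion called here only | no feedback step | Confirmed only if existing data cover it |
| Otherwise | 5.5 item 3 | False positive |

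5.1 item 5 counts unequivocal evidence on both conventional imaging and PET as a true positive, which would shield concordant lesions. 5.5 item 1 does not repeat that rule. The exposed calls are therefore mainly discordant or equivocal ones.

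**3. Baseline for an illustration.** The retrospective series of 176 patients cited in 1.2.1 reports sensitivity 93%, specificity 76%, PPV 91% and NPV 81%. Solving PPV = 0.93p / [0.93p + 0.24(1 − p)] = 0.91 gives p = 0.2184 / 0.3021 = 0.723. Per 100 men: TP 67.23, FN 5.06, FP 6.65, TN 21.06. Check: NPV = 21.06 / 26.12 = 80.6%, as reported.

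**4. Effect of item 3.** Assumptions that are not in the documents: u = 3 to 8 men per 100 are positive on the study read only, none is confirmed by existing data, and a share t = 50–90% of them truly have metastasis. Misscored men are m = u × t, from 3 × 0.5 = 1.5 to 8 × 0.9 = 7.2.

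| | Formula | m = 0 | m = 1.5 | m = 7.2 |
|---|---|---|---|---|
| PPV | (67.23 − m) / 73.88 | 91.0% | 89.0% | 81.3% |
| Specificity | 21.06 / (27.71 + m) | 76.0% | 72.1% | 60.3% |
| Sensitivity | (67.23 − m) / (72.29 − m) | 93.0% | 92.9% | 92.2% |
| Confirmed, PET-positive men | 67.23 − m | 67.2 | 65.7 | 60.0 |

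NPV is unchanged. If t = 0, then m = 0 and item 3 scores these calls correctly.

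**5. Which modality is affected more?** Take the 15% and 35% in 5.5's example as true positives per 100. Assume 50 men truly metastatic and 2 other false positives per modality (neither figure is in the documents), with a share s of true positives seen only at the study read and left unconfirmed.

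| s | Conventional: added FP, specificity, PPV | PET: added FP, specificity, PPV |
|---|---|---|
| 0 | 0, 96.0%, 88.2% | 0, 96.0%, 94.6% |
| 10% | 1.5, 93.2%, 79.4% | 3.5, 89.7%, 85.1% |
| 20% | 3.0, 90.6%, 70.6% | 7.0, 84.2%, 75.7% |

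At an equal share PET gains more false positives. Conventional imaging gains more, and loses more specificity, only if its share exceeds 35/15 = 2.3 times the PET share. For PPV the fall is s × 15/17 = 0.88s against s × 35/37 = 0.95s, so there the break-even ratio is only about 1.07. No figure in the documents bears on the two shares.

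**6. What the fix would report.** With u = 8 and t = 0.9, counting all eight as true positives moves the 0.8 false calls across: PPV = 68.03 / 73.88 = 92.1%, specificity = 21.06 / 26.91 = 78.3%. Counting all eight as false positives gives 81.3% and 60.3%. The ranges contain the assumed 91% and 76%. For these men, item 3 as written reports only the lower end.

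**The case against.** The strongest reply is that late calls are not without recourse. Item 10 compares the reviews with histology or post-treatment images already gathered, and 5.5 item 1 also accepts response to androgen suppression or other therapy. Nothing restricts the post-treatment images to lesions named in the clinical report. If scoring is per patient, another confirmed lesion makes the man a true positive. All of this stands, so a reader should not infer that every study-read-only lesion becomes a false positive. It is so only where existing data do not confirm it, and 5.1 item 6 does not guarantee that such data exist.

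A second reply is that no passage ties confirmation to the clinical report. That is right. It is an inference from the order of events in 5.1 and 5.4.1, though no other order is described.

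A reader might also infer that conventional imaging is hit hardest, because a CT or MRI finding without uptake would be set aside clinically, and hence that the comparison tilts towards PET. The documents do not support this. 5.1 item 5 has CT and MRI evaluated in their own right and puts evidence on conventional imaging or PET within the confirmation rule. The low PET threshold in 5.4.2 (focal uptake above background) could itself produce late PET calls. Step 5 shows that the direction depends on shares nobody has given.

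Finally, the size rests on assumed inputs and on one retrospective series with about 74 PET positives per 100, whereas 5.5's example expects 35. That also stands.

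**Conclusion.** The point holds in a limited form. Scored reads come after care and follow-up have ended, and 5.5 item 3 has no place for a positive that could not be assessed. Followed as written, the plan can count true lesions as test errors and so lower PPV, specificity and the rate of confirmed metastasis for each modality.

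The direction of any effect on the comparison between modalities is unknown. The size is illustrative only: PET PPV 81–89% instead of 91% and specificity 60–72% instead of 76%. This requires 3–8 men per 100 positive on the study read only, 50–90% of them truly metastatic, none rescued by existing data, and scoring per man. It is a defect in the scoring rule that should be put right before the reads are analysed. It does not invalidate the design.

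**What to change.** Change 5.5 item 3 so that a positive is a false positive only when the reference information gathered for that patient was able to assess it and did not confirm it. Then:

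- Put positives with no such assessment, including those called only on the end-of-study read, in a separate unverified category, and report their number by modality.
- Report sensitivity, specificity, PPV, NPV and the paired comparison twice, with unverified positives counted all as true positives and all as false positives. Do not simply drop them from the false-positive count, as that would flatter PPV and specificity.
- State whether the unit of analysis is the patient or the lesion.
- Record for each scored lesion whether it was in the clinical report.

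No extra work-up of study-read lesions is asked for; that could mean more biopsies or scans. The cost is one more recorded item per lesion, a second run of the analysis, and accuracy reported as a range, which will be wide if many positives are unverified.

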5.4.2 Image Assessment Criteria

The following image criteria will be documented with each patient study utilizing the worksheets included as attachments in appendix A3.0.

- Lesion considered positive if there is focal uptake greater than background.
- Faint uptake within inguinal nodes considered normal.
- Retroperitoneal lymph nodes >1 cm in short axis diameter considered positive.
- Record CT abdomen and pelvis as follows:
 1. Report mass within prostate or prostate bed
 2. Report retroperitoneal lymph nodes with >1 cm short-axis measurement
 3. Report bone metastases
 4. Report any other metastatic disease (liver, lung, etc)
- Record PET/CT as follows:
 1. Study quality (adequate, non-diagnostic)
 2. Positive lymph nodes.
 - Pelvic or retroperitoneal lymph nodes >1 cm.
 - Radiotracer uptake in lymph node any size
 3. Bone metastases
 - Radiotracer uptake
 - CT abnormality
 4. Other metastatic disease (liver, lung, etc.)
 - Radiotracer uptake
 - CT abnormality
 5. Confidence of diagnosis: 3 – 1
(Rating: 3 – Definitely Present, 2 – Probably Present, 1 – Equivocal)
- Record PET/MRI:
 1. Study quality (adequate, non-diagnostic)
 2. Positive lymph nodes.

- Retroperitoneal lymph nodes >1 cm.
- Radiotracer uptake any size lymph node
- DWI positive
- 3. Bone metastases
 - Radiotracer uptake
 - T2 or DWI positive
- 4. Other metastatic disease (liver, lung, etc.)
 - Radiotracer uptake
 - T2 or DWI positive
- 5. Confidence of diagnosis: 3 – 1
(Rating: 3 – Definitely Present, 2 – Probably Present, 1 – Equivocal)

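### Section 5.4.2 gives the conventional comparator no MRI-alone record and a narrower CT record than PET/CT, which risks under-counting conventional detection and overstating the PET gain

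*Combined protocol and SAP*

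**What the plan says.** All references are to the comparison protocol, not to the expanded-access protocol bound with it.

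- **What is compared.** Section 5.5 sizes the study to set the fused scans "against a standard CT scan and MRI scan". Data Analysis item 5 plans "Sensitivity, specificity, PPV, and NPV of CT and MRI and of" the PET fusions. Section 5.1 step 5 has CT and MRI evaluated for metastasis and compares confirmed rates with PET. Section 5.6 promises to publish that comparison.
- **What is acquired.** Section 5.2 specifies "CT skull base to mid thigh for attenuation correction", and PET covers the same range. MRI has coronal T2 over that range, axial T2 of the prostate bed and DWI of the pelvis. Section 4.1.1 leaves men who cannot have MRI out of the comparison data, so MRI should exist for everyone in it.
- **What is recorded.** Section 5.4.2 lists three records. The first is introduced by "Record CT abdomen and pelvis as follows" and its node item is "Report retroperitoneal lymph nodes with >1 cm short-axis measurement". The PET/CT node item is "Pelvic or retroperitoneal lymph nodes >1 cm", plus uptake in a node of any size; CT abnormality is a sub-item for bone and other disease. The third record is PET/MRI, where the T2 and DWI findings sit. No record is for MRI alone.
- **Where the reads are held.** Section 5.4.2 refers to worksheets in appendix A3.0, which is not in the text supplied.

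**The concern.** The main comparison needs a conventional result built from CT and MRI. The stated recording list supplies a CT result only, with a narrower heading and fewer node stations than the PET/CT record applied to the same CT images. An enlarged pelvic node has an entry under PET/CT but no node entry under CT. A lesion seen only on T2 or DWI has an entry only inside PET/MRI.

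If the analysis uses the list as it stands, part of any difference in detection would come from what the form allowed the comparator to count, not from the tracer. The scanner does not impose this, since the images are acquired over the full range. The quantity at risk is detection rate, which the sample size is built on, and with it sensitivity.

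**Working it through.** **1. The plan's own figure.** Inputs from 5.5: significance level 0.05 (two-sided assumed, since sidedness is not stated), power 80%, paired chi-square test, rates of 4% and 20%. Read the two rates as the discordant cells, so p_d = 0.24 and d = 0.16:

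n = (1.960 + 0.842)² × (p_d − d²) / d² = 7.849 × (0.24 − 0.0256) / 0.0256 = 65.7, so 66.

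Enumerating the uncorrected paired test at n = 66 gives power 0.80. The stated 66 pairs reproduces. It is not affected by this point, which concerns how the comparator is measured.

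**2. The records side by side (5.4.2).**

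| Item | CT record | PET/CT record | PET/MRI record |
|---|---|---|---|
| Region named in heading | Abdomen and pelvis | None | None |
| Nodes by size | Retroperitoneal | Pelvic or retroperitoneal | Retroperitoneal |
| Other node evidence | None | Uptake, any size | Uptake, any size; DWI |
| Bone | Yes, no region stated | Uptake; CT abnormality | Uptake; T2 or DWI |
| Other metastases | Yes, lung named | Uptake; CT abnormality | Uptake; T2 or DWI |
| Prostate or bed mass | Yes | No | No |
| MRI alone | No such record | – | – |

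Two gaps are clear: MRI alone, and pelvic nodes on CT. A third, disease above the abdomen, is only possible, because the heading and the listed items point different ways.

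**3. Direction.** If a conventional positive can come only from the CT record, leaving out findings can only lower the conventional detection rate and sensitivity. The same omission also removes any conventional false positives among those findings, so conventional specificity can rise.

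**4. Size, under an assumption.** Let f be the share of men positive on conventional imaging whom the list misses. The documents do not give f. Assume 10–30%, with the PET result unchanged. Apparent gain = PET rate − conventional rate × (1 − f). The 15% and 35% are the example in 5.5. The 50% is the approximate literature rate in 5.5, with the 20-point goal added.

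| f | 15% v 35%: recorded conventional | Apparent gain | 50% v 70%: recorded conventional | Apparent gain |
|---|---|---|---|---|
| 0 | 15.0% | 20.0 | 50% | 20 |
| 10% | 13.5% | 21.5 | 45% | 25 |
| 20% | 12.0% | 23.0 | 40% | 30 |
| 30% | 10.5% | 24.5 | 35% | 35 |

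**5. Effect on the test if there is no true gain.** Assume both rates are 35% with 4% discordant each way, so 31% are positive on both, and that losses are unrelated to the PET result. Then the PET-only cell = 4 + 31f and the conventional-only cell = 4(1 − f), in percentage points. Rejection probability is for the uncorrected paired test at n = 100, two-sided 0.05, by enumeration.

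| f | PET-only | Conventional-only | Spurious gain | P(reject) |
|---|---|---|---|---|
| 0 | 4.0% | 4.0% | 0 | 0.045 |
| 10% | 7.1% | 3.6% | 3.5 | 0.168 |
| 20% | 10.2% | 3.2% | 7.0 | 0.480 |
| 30% | 13.3% | 2.8% | 10.5 | 0.785 |

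These are illustrations of sensitivity to f, not estimates.

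**The case against.** The strongest reply is that the controlling document is unseen. The appendix A3.0 worksheets may hold a full CT and MRI read. Section 5.1 step 5 plans evaluation of CT and MRI separately from the PET images, and 5.5 items 1 and 3 treat conventional CT or MRI as a source of positives in its own right. A reader might infer that MRI is never scored without PET and that the comparator is certainly under-counted. The documents do not support that certainty. What stands is that 5.4.2 is where the criteria are stated, and it states none for MRI alone.

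Other replies, and what remains of each:

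- **The CT record may not be confined to abdomen and pelvis.** Its last item is "Report any other metastatic disease (liver, lung, etc", which names lung, and its bone item has no region limit. This stands: the scope is unclear, not closed. It does not touch the pelvic-node or MRI gaps.
- **MRI findings might be extracted from PET/MRI.** T2 and DWI have their own sub-items there, so it goes too far to say item 5 could not be computed for MRI. But nothing says those entries are made without sight of PET, and PET-guided entries could raise the conventional rate.
- **The bias need not always favour PET.** Specificity could move against it, and only the CT record lists a prostate or prostate-bed mass. This stands; the direction claimed here is for detection of metastasis and sensitivity.
- **The 31-patient study in 1.2.1 does not size the problem.** It reports local relapse in 12 men on PET/MRI and 8 on PET/CT: 12/31 − 8/31 = 12.9 points. A reader might subtract some of that from 20 and conclude that the gain over CT plus MRI is only 7–15 points. Both arms of that study include PET and the count is of local relapse, whereas this trial targets metastasis. It does not measure what MRI alone adds to CT alone.

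**Conclusion.** The point holds as a risk, conditional on the conventional result being taken from the 5.4.2 list. On that condition, MRI-only and pelvic-node findings are left out of the comparator, and findings above the abdomen may be. Conventional detection and sensitivity would then be too low and the PET gain too large; specificity could shift in the opposite direction.

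The size is not derivable from the documents. With an assumed 10–30% of conventional positives missed and PET unaffected, a true 20-point gain at 15% versus 35% would appear as 21.5–24.5 points. The distortion grows with the conventional rate. With no true gain and both rates at 35%, the same losses would raise the rejection probability at n = 100 from 0.045 to between 0.168 and 0.785.

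The gap should be closed before the end-of-study read, because the comparator is otherwise not defined as a scored result.

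**What to change.** In section 5.4.2 and the appendix A3.0 worksheets:

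1. Add separate CT-alone and MRI-alone records, completed by the same radiologists without PET and before they see the fused images. Section 5.4.1 presents studies in random order, so state that the random order applies within each reading round.
2. Have both records cover the acquired field, with the same regions and node stations as the PET records, including pelvic nodes. Align the size-based node item in PET/MRI, which is retroperitoneal only.
3. Use the T2 and DWI criteria already listed for the MRI-alone record. DWI is acquired in the pelvis only, so elsewhere the record rests on T2.
4. In 5.5, score a patient as conventional positive if either the CT-alone or the MRI-alone record is positive.

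If the worksheets already do this, bringing 5.4.2 into line with them is enough. No new imaging is needed, since the scans are already acquired and section 5.4.1 places the formal review at the end of the study. The cost is a worksheet revision, somewhat longer reading time, and probably a smaller PET advantage.

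### A pelvic node over 1 cm without tracer uptake counts as positive on PET/CT but falls outside the CT nodal rule, although only one CT is described for both reads

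*Combined protocol and SAP*

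**What the plan says.** All references are to the comparison protocol within the combined document, not to the expanded-access protocol that follows it.

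Section 5.4.2 states nodal size four times:

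- **General rule:** "Retroperitoneal lymph nodes >1 cm in short axis diameter considered positive".
- **CT record**, headed "Record CT abdomen and pelvis as follows": item 2 is "Report retroperitoneal lymph nodes with >1 cm short-axis measurement". Item 4 is an open item: "Report any other metastatic disease (liver, lung, etc".
- **PET/CT record**, under positive lymph nodes: "Pelvic or retroperitoneal lymph nodes >1 cm", then on a separate line "Radiotracer uptake in lymph node any size".
- **PET/MRI record**, under positive lymph nodes: "Retroperitoneal lymph nodes >1 cm", then "Radiotracer uptake any size lymph node", then DWI positivity.

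There is no record for MRI without PET. The criteria are to be documented on worksheets in Appendix A3.0, which is not in the text supplied.

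Sections 5.1 (item 5), 5.2 and 5.3 describe a single CT. It is acquired in the PET/CT protocol, fused with the PET, and done in one continuous session with the MR.

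Three planned analyses use these reads:

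- Section 5.1 item 5 compares confirmed metastasis rates on conventional CT and MRI with those on the choline PET images.
- Section 5.5 Data Analysis item 5 calculates accuracy for CT and MRI and for the choline scans.
- Section 5.5 Data Analysis item 6 compares PET/CT with PET/MRI.

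**The concern.** In a paired comparison of imaging methods, a difference between reads should come from what the methods show. Here it can also come from what each form asks the reader to score. An enlarged pelvic node without uptake looks the same on the CT read and on the CT component of the PET/CT read. Only the PET/CT list names it.

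If the CT reader follows the nodal line and does not use item 4, that patient is discordant in favour of PET/CT with no contribution from 11C-choline. What follows depends on confirmation under section 5.5:

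- If the node is confirmed, PET/CT gains a true positive and CT takes a false negative (item 4).
- If it is not confirmed, PET/CT takes a false positive (item 3), and its specificity and PPV fall.

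In both cases the estimate reflects the scoring list. The size and uptake lines are separate on PET/CT, so the affected patients could be identified if each line is recorded. The plan does not say that this will be done or that uptake-based positivity will be reported alone.

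**Working it through.** **Step 1. The rules side by side.**

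| Read | Territory in the size line | Axis stated | Other route for a pelvic node |
|---|---|---|---|
| General rule | Retroperitoneal | Short axis | Focal uptake above background |
| CT | Retroperitoneal | Short axis | Item 4 only; names no nodes, sets no size |
| PET/CT | Pelvic or retroperitoneal | No | Uptake, any size |
| PET/MRI | Retroperitoneal | No | Uptake, any size; DWI |
| MRI without PET | No record | No record | No record |

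**Step 2. Is size alone enough on PET/CT?** Uptake counts in a node of any size. If the size line also needed uptake, it would add nothing to the uptake line. It has a function only if size is sufficient by itself.

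**Step 3. The plan's own figure.** Section 5.5 gives about 66 pairs at alpha 0.05 and 80% power. With its 20% and 4% used as the two discordant proportions (sum s = 0.24, difference d = 0.16) and a two-sided test, n = (1.960 + 0.842)² × (s − d²) / d² = 7.849 × 0.2144 / 0.0256 = 65.7, so 66. The figure reproduces. It does not help to size this problem, because it concerns fused scans against CT and MRI together.

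**Step 4. Size of the artefact, CT alone versus PET/CT.** The documents give no rate, so all three inputs are assumptions:

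- f, patients whose only finding is a pelvic node over 1 cm without uptake: 1% to 5%.
- u, share not reported under CT item 4: 50% to 100%.
- v, share confirmed, where only confirmed findings count: 50% to 100%.

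The artefact is g = f × u × v.

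- Low: 1% × 0.5 × 0.5 = 0.25 points, and 0.25 / 20 = 1.25% of the goal.
- High: 5% × 1 × 1 = 5 points, and 5 / 20 = 25% of the goal.

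**Step 5. A threshold that needs no rate.** Take 100 pairs and no tracer gain. Let c be the background discordant pairs in each direction and x the patients discordant only because of the rule. The table gives the smallest x at which McNemar's test has two-sided p < 0.05.

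| c each way | Uncorrected | Exact |
|---|---|---|
| 0 | 4 (p = 0.0455) | 6 (p = 0.0312) |
| 2 | 7 (p = 0.0348) | 8 (p = 0.0386) |
| 4 | 8 (p = 0.0455) | 9 (p = 0.0490) |

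**Step 6. Chance of a significant PET/CT gain when the tracer adds nothing.** There are 100 pairs. Discordance favouring PET/CT has probability background + g, and discordance favouring CT has probability background. The background is assumed. Entries are exact / uncorrected.

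| g (points) | Background 4% each way | Background 2% each way |
|---|---|---|
| 0 | 0.9% / 2.2% | 0.3% / 2.1% |
| 0.25 | 1.2% / 2.7% | 0.4% / 2.9% |
| 1.25 | 2.8% / 5.2% | 2.1% / 7.1% |
| 2.5 | 6.4% / 10.2% | 6.9% / 14.7% |
| 5 | 19.7% / 26.8% | 26.2% / 36.9% |

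**Step 7. PET/CT versus PET/MRI.** The size lines differ here too, but PET/MRI can score a pelvic node by uptake or DWI. The direction is uncertain, so no figure is given.

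**The case against.** The wording mismatch is hard to dispute. The case on the other side concerns its weight.

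- **The sized comparison is a different one.** It sets the fused scans against CT and MRI together, and axial DWI of the pelvis and whole-body coronal T2 are acquired. If the node is called on MRI, the conventional side is credited and the artefact disappears. This stands: no effect on the sized comparison has been shown. It has not been excluded either, because no rule for MRI without PET is listed.
- **CT item 4 could capture the node, and nothing calls it negative on CT.** This also stands. A CT false negative is possible, not forced. But naming pelvic nodes on one form and leaving them to discretion on the other is still unequal.
- **The A3.0 worksheets may already be uniform.** They may be. In that case they conflict with section 5.4.2, and the text still needs correcting.
- **The magnitude rests on assumptions and on zero tracer gain.** With true discordance of 20% and 4%, exact McNemar power at 100 pairs is 0.91 with no artefact, 0.94 with 1.25 points added and 0.98 with 5. If the tracer works as planned, the test decision barely changes. The estimated difference would still shift by g.
- **The bias does not always favour PET/CT.** An unconfirmed node counts against PET/CT in specificity and PPV. That is correct, and it is a distortion from the same source.

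That one CT serves both reads is inferred from sections 5.1 to 5.3. No sentence says so outright, but no other study CT is described.

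**Conclusion.** The concern holds and should be fixed. As written, section 5.4.2 can score the same anatomy as positive on PET/CT and leave it unreported on CT, in reads that the plan compares within patients.

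For CT alone against PET/CT, the artefact is 0.25 to 5 points under the assumed f, u and v. At the low and middle of that range the rule alone is unlikely to produce a significant result. At 5 points the chance is about 20% to 27% with a 4% background each way, and 26% to 37% with 2%. The true rate of such patients is unknown.

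None of these figures applies to the sized comparison with CT and MRI, where the effect cannot be determined from the text. For PET/CT against PET/MRI the direction is uncertain. Confidence is medium, mainly because the worksheets were not available and the rates are assumed.

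**What to change.** In section 5.4.2 and the A3.0 worksheets, apply the same nodal territories (pelvic and retroperitoneal) and the same over-1-cm short-axis rule to CT, MRI, PET/CT and PET/MRI. Keep size and uptake as separately recorded fields. State in section 5.5 that uptake-based positivity will be reported on its own.

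A useful addition is a record for MRI without PET, with its own criteria, based on the T2 and DWI images already acquired. Section 5.5 item 5 needs one. The harmonised size rule is worth making even without it.

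The cost is an edit to one criteria list, the worksheets and one line of section 5.5. Images and readers stay the same. Section 5.4.1 places the research read at the end of the study, so no patient is rescanned. Reads become slightly longer, and the PET/CT advantage over CT may look smaller.
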